Official Title of the study: ADDRESS: Activity Dependent Rehabilitation via Transcutaneous Electrical Spinal Stimulation to Restore Upper Extremity Functions in Spinal Cord Injury

NCT number: NCT03184792

Date of the document: February 22, 2022

Study Protocol:

Spinal cord injury and other spinal dysfunctions have a lifelong, high impact on individuals, families, and society. It is estimated that there are between 250,000 and 500,000 new cases of spinal cord injury each year, worldwide. Spinal cord injury is currently incurable. Existing treatment options are less than satisfactory and are limited to preventing secondary complications and maximizing residual function through rehabilitation. Paralysis of the upper limbs results in a significant loss of independence in daily activities and a decrease in quality of life. Tetraplegic patients suffering from a cervical spinal cord injury prioritize the recovery of their arm and hand function to enhance quality of life.

Stimulation of the spinal cord may induce the growth and reorganization of neural pathways, leading to the reanimation of paralyzed limbs. To date, epidural stimulation with surgically implanted electrodes is demonstrating tremendous success for patients with spinal cord injury. Growing evidence suggests that electrical spinal stimulation modulates the excitability of spinal circuitry, enabling the weak but remaining descending drive (signal pathways from the brain) to resume control of movements. Utilizing epidural stimulation can enhance conscious motor control in both the legs and hands of human subjects. Even in cases of clinically complete spinal cord injury, initiation of voluntary leg movements and gains in postural control are observed in human subjects. In addition, epidural stimulation results in tonic and rhythmic motor patterns in the lower limbs of humans lying supine, as well as improvements in bowel, bladder, and sexual function.

Recently, a non-invasive technique for spinal stimulation, specifically transcutaneous electrical spinal cord stimulation, has been demonstrated to be effective in improving motor function in both healthy individuals and patients with spinal cord injuries. The effects of this novel technology on upper extremity motor function have not been tested. This research study employs a prospective, experimental, randomized crossover design to assess the safety and efficacy of transcutaneous cervical electrical stimulation in improving upper limb function in patients with cervical spinal cord injury.

Electrical cervical stimulation has been shown to be effective in improving upper limb function in animal studies conducted in our laboratory. By other groups, transcutaneous electrical spinal

cord stimulation has been demonstrated to be effective in improving lower extremity motor function in both healthy individuals and patients with spinal cord injury. Transcutaneous spinal stimulation was applied to the skin via external electrodes placed midline on the spinous processes of the vertebrae. A novel, well-tolerated, and painless transcutaneous electrical enabling motor control strategy was used for neuromodulation. Previously, no adverse effects have been reported with transcutaneous electrical spinal cord stimulation. Patients described a non-disturbing tingling sensation beneath the electrodes.

The purpose of the study is to implement and test transcutaneous spinal stimulation in patients with cervical spinal cord injury (traumatic or degenerative etiology) in combination with a rehabilitation program. We aim to enhance both arm and hand sensorimotor functions.

Our primary objectives are:

1. To establish a novel, non-invasive therapeutic stimulation approach in patients with cervical spinal cord injury.
2. To determine transcutaneous stimulation locations and parameters that are safe and effective for augmenting hand motor and sensory function.
3. To evaluate both immediate and lasting improvements in hand motor and sensory function via transcutaneous cervical spinal stimulation.

Our secondary objectives are to document and analyze other potential benefits of electrical neuromodulation, including a decrease in spasticity, an increase in bowel and bladder control, and an improvement in mobility.

Inclusion Criteria. Individuals who

1. has cervical (C7 or higher) spinal cord injury with a duration of at least 1 year duration
2. are between 21 and 70 years of age
3. has difficulty with hand functions in activities of daily living (e.g., dressing, grooming, feeding)
4. has a stable medical condition without cardiopulmonary disease or frequent autonomic dysreflexia that would contraindicate participation in upper extremity rehabilitation or testing activities
5. are capable of performing simple cued motor tasks
6. has the ability to attend 2 to 5 weekly physical therapy sessions and testing activities
7. has adequate social support to be able to participate in weekly training and assessment sessions for the duration of 6 months within the study period.
8. has the ability to read and speak English

will be included in the study.

Exclusion criteria. Individuals who

1. has an autoimmune etiology of spinal cord dysfunction/injury
2. has a history of additional neurologic disease, such as stroke, MS, traumatic brain injury, etc.
3. has peripheral neuropathy (diabetic polyneuropathy, entrapment neuropathy, etc.)
4. has rheumatic diseases (such as rheumatoid arthritis and systemic lupus erythematosus)
5. has significant medical disease, including uncontrolled systemic hypertension with values above 170/100 mmHg; cardiac or pulmonary disease; chronic contagious disease, such as Hepatitis B and C, HIV; uncorrected coagulation abnormalities or need for therapeutic anticoagulation.
6. has active cancer
7. has cardiovascular or musculoskeletal disease or injury that would prevent full participation in the physical therapy intervention
8. unhealed fracture, contracture, pressure sore, urinary tract infection, or other illnesses that might interfere with upper extremity rehabilitation or testing activities
9. has any condition that would render the patient unable to safely cooperate with the study tests, as judged by the screening physician
10. are pregnant
11. has received botulinum toxin injections in the upper extremity muscles in the prior 6 months
12. has undergone tendon transfer or nerve transfer surgery in the upper extremity
13. are dependent on ventilation support
14. has an implanted stimulator (e.g., vagus nerve stimulator, pacemaker, cochlear implant, etc.).
15. has depression or anxiety based on Patient Health Questionnaire (PHQ-9) (score >9/27) and General Anxiety Disorder-7 item Questionnaire (score >9/21), respectively.
16. has alcohol and/or drug abuse.
17. has cognitive impairment based on the Short Portable Mental Status Questionnaire (SPMSQ) (score >2/10).
18. are unable to read and/or comprehend the consent form.
19. lack of ability to fully comprehend and/or perform study procedures in the investigator's opinion/judgement
20. has a history of severe allergy (i.e., allergic reaction that could not be treated with antihistaminic medication

will be excluded.

[figure not shown]
If a patient inquires about the study, they will then be provided an opportunity to speak with research assistants about the study. This will be done in a quiet and private area, such as a patient's room or office, in order to maintain confidentiality. If the patient contacts us via phone, research assistants will provide information about the study and answer their questions.

Research assistants will explain that participation in the study is strictly voluntary, and if the patient chooses not to enroll, their care will not be affected in any way. The research team member obtaining informed consent will explain that participation in the experiment is not required nor connected with the clinical treatment or procedure. No individual incentives will be offered in exchange for participation in the study.

Subjects who meet all the inclusion criteria and none of the exclusion criteria at their pre-screening and initial evaluation visit will be approached by research assistants. (S)he will explain the study and review the consent with the patient. Patients will be assured that participation is voluntary and that they will continue to receive their usual clinical care if they choose not to participate. Subjects will be given 1 week to decide whether they wish to participate in the study.

We will use advertisement flyers/information sheets that will be clearly displayed in the neurosurgery and rehabilitation outpatient departments for all to see. Additionally, subjects will be informed about the study during their routine control visits in the Departments of Neurosurgery and Rehabilitation Medicine by their primary physicians. Notifications may be posted on our departmental and laboratory websites and distributed via listservs that reach this community.

Study design:

Week 1 2 3 4 5

Timeline for outcome measurements:
Weeks without asterisk – only GRASSP quantitative prehension and grip & pinch strength measurements will be done

A Physical Therapy Only

A – Physical Therapy Only

Pre-Screening Phase – Patients interested in volunteering will be evaluated for eligibility by a research assistant. Candidate patients will be asked to provide their oral consent to participate in the screening questionnaires. This includes a yes-no questionnaire and multiple-choice questions by phone or in person.

After completing the screening procedures, eligible patients will provide informed consent.

During that visit, one of the research assistants will answer any further questions the candidate patient may have regarding the study. Patients will have 1 week to decide whether they would like to participate in the study.

Phase I – Initial Medical Assessment and Baseline Measurements

After obtaining informed consent, an initial medical assessment of the included subjects will be conducted by a licensed physician/neurosurgeon of our UW Neurological Surgery Department. Baseline upper extremity functional measurements and health-related questionnaires will be obtained by one of the research assistants/scientists at the UW Department of Rehabilitation Medicine and/or the Amplifying Movement & Performance Laboratory (AMP Lab). [name]. Initial medical assessment and outcome measurements include:

- A complete physical and neurological exam
- Graded and Redefined Assessment of Strength, Sensibility, and Prehension Test (GRASSP)
- International Standards for Neurological Classification of Spinal Cord Injury (ISNCSCI)
- Hand strength measurement by grip and pinch dynamometry
- WHO-Quality of life – BREF

After the initial assessment, patients will be scheduled for additional hand function measurements up to 2 times per week for up to 4 weeks (no more than four sessions total). These sessions measure the stability of the underlying disability and control for test-retest learning. Each session will last 1-2 hours. These recurrent measurements will include:

- GRASSP test Quantitative Prehension Subscale
- Vital signs (blood pressure, heart rate)
- Hand strength measurement by grip and pinch dynamometry

Phase II – Intervention Phase

After Phase I, patients will be randomized to receive either physical therapy alone (Arm A) or physical therapy plus transcutaneous spinal cord stimulation (Arm B) for 6 weeks. Then, patients will be followed up for an 8-week wash-out period, during which neither study intervention will be administered. During wash-out period, patients will not be allowed to receive treatments that violate exclusion criteria (e.g., botulinum toxin injections or tendon/nerve transfer

surgery in the upper extremity) or new treatments that could affect the study's outcome (e.g., alternative exercise therapies or robotic rehabilitation targeting upper extremity function).

However, they can continue to get their regular lower extremity physiotherapy.

Next, the intervention arms will be crossed over, i.e., patients who received the A intervention arm first will receive the B intervention arm, and vice versa, for another 6 weeks. In each intervention arm, sessions will last 2 hours/day, 2-5 days/week.

Transcutaneous Spinal Cord Stimulation Procedure: Transcutaneous spinal electrical stimulation is a non-invasive neurostimulation technique. Stimulation will be delivered through the skin using surface hydrogel electrodes, which are commonly used in practice today.

During the first stimulation session, optimal electrode placement and stimulation parameters will be determined using hand function testing and electromyographic (EMG) testing of the upper extremity muscles. Hand function will be tested by the abbreviated GRASSP test, Quantitative Prehension subscale, pinch and grip force measurements, and Capabilities of Upper Extremity Test (Cue-T). EMG testing will be done using skin surface recording electrodes.

Transcutaneous spinal stimulation paradigms that elicit appropriate muscle activation with the lowest threshold stimulation current will be identified. A painless cutaneous enabling motor control paradigm will be used for this purpose: biphasic or monophasic rectangular pulses of 1.0 ms per phase duration will be delivered at a frequency of approximately 30 times per second (Hz). Within these pulses, a very high carrier frequency of 10 kHz is delivered to avoid painful sensations as the current crosses the skin (i.e., the Russian Method of muscle stimulation). Stimulation intensity will range from 1 to 180 mA. During the initial testing, stimulation will be delivered for a duration of 10 to 30 seconds.

After determining the optimal initial stimulation configuration, we will deliver physical therapy sessions while transcutaneous spinal stimulation is administered for a total of up to 90 minutes. The duration of 90-minute stimulation is determined based on the effect mechanism and safety information reported in earlier clinical studies with spinal stimulation. Time without stimulation will be interspersed to examine the difference in movement with and without stimulation.

Hand and Arm Physical/Occupational Therapy Protocol: The therapy program will include progressive functional task practice for upper extremity motor training (i.e., active assistive range of motion, stretching, strengthening, reaching and grasping exercises, and fine motor skills training). The physical therapy program will be tailored to the patient's specific functional deficits and needs.

For safety monitoring, we will document vital signs (blood pressure, pulse, respirations, temperature), orientation to time and place, and skin examination before and at the end of each

session. For cardiovascular safety, non-invasive continuous blood pressure monitoring will be done during transcutaneous cervical spinal electrical stimulation. Patients will be encouraged to report any abnormal feelings and discomfort throughout the session. After each session, patients will be released if they are deemed stable. If not, they will be referred to a healthcare professional for evaluation and provided appropriate care.

Every two weeks throughout the intervention, we will measure and document the functional improvements observed during stimulation and those that persist beyond the stimulation. At the end of each intervention arm and wash-out period, outcome measurements will be repeated, as described in the study design figure above.

Phase III – Follow-up

After completing the two-arm crossover intervention phase (Phase II), patients will be provided with a home rehabilitation exercise program. Three follow-up visits during the early follow-up period (8 weeks following the last intervention session) and one last follow-up visit at the end of one year of the study will be scheduled, where assessments and measurements will be done as described in the study design figure above, at UW Rehabilitation Department and/or in Amplifying Movement & Performance Laboratory.

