Official Title of the study: ADDRESS: Activity Dependent Rehabilitation via Transcutaneous Electrical Spinal Stimulation to Restore Upper Extremity Functions in Spinal Cord Injury

NCT number: NCT03184792

Date of the document: February 22, 2022

Statistical Analysis Plan:

For comparison of the functional changes occurring during each intervention phase, one-way repeated measures ANOVA will be used with post-hoc pairwise analysis as per Tukey LSD test (IBM SPSS version 26). A Shapiro-Wilk Test will be used to determine whether repeated measurements follow a normal distribution. Mauchly's test will be used to analyze the assumption of sphericity, and degrees of freedom will be corrected using Greenhouse-Geisser estimates of sphericity when the assumption is violated. We will directly compare the benefits of training alone and stimulation combined with training by calculating the cumulative changes in each outcome measure across the two intervention arms. These values will be normalized to baseline to control for individual variation in function at the beginning of the study and compared between the training and stimulation + training interventions using a paired-samples T-test.

Additionally, score changes relative to the preceding treatment block will be calculated to compare the improvement rates between intervention phases repeated monthly. For all tests, $p < 0.05$ will be considered significant. All participants' data will be included in all analyses. Given the early stage of research and the lack of prior data on transcutaneous spinal cord stimulation for restoring upper limb function, power analysis and sample size calculations are not feasible.

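### The paired B-versus-A contrast has no protection against unequal carryover and no defined starting point for the period-2 change, in a trial that looks for lasting benefit

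*Protocol*

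**What the plan says.** Under Phase II – Intervention Phase, the protocol randomises patients to physical therapy alone (A) or with stimulation (B) for 6 weeks. Then "patients will be followed up for an 8-week wash-out period, during which neither study intervention will be administered", after which "patients who received the A intervention arm first will receive the B intervention arm, and vice versa, for another 6 weeks". No return-to-baseline condition is attached, and the text gives no reason for 8 weeks.

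The protocol also looks for durable effects:
- The background proposes that "Stimulation of the spinal cord may induce the growth and reorganization of neural pathways".
- Primary objective 3 is "To evaluate both immediate and lasting improvements in hand motor and sensory function via transcutaneous cervical spinal stimulation".
- During treatment, every two weeks, "we will measure and document the functional improvements observed during stimulation and those that persist beyond the stimulation".
- Phase III follows patients for 8 weeks after the last session, with a final visit at one year of the study.

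Outcomes are measured again at the end of each arm and at the end of wash-out.

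The SAP calculates cumulative changes in each arm and normalises them to baseline to account for function at the start of the study. These are then "compared between the training and stimulation + training interventions using a paired-samples T-test". It adds a comparison of improvement rates based on change from the preceding treatment block. It names no sequence, period or carryover term, no period-1 comparison, and no use of the end-of-wash-out measurement as a reference or check.

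**The concern.** In a two-period crossover, the within-person contrast estimates the treatment effect only if what is left over from period 1 does not differ between the sequences in the quantity compared. Here one sequence enters period 2 after training and the other after training plus stimulation. If stimulation adds a lasting gain, the second group carries more into its training-alone period. When outcomes are judged against study baseline, that surplus is credited to training alone and shrinks the B-minus-A difference.

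A small crossover difference could then mean that stimulation adds little, or that its benefit persisted. The planned analyses would not separate the two, although persistence is one of the things the trial sets out to find.

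**Working it through.** The documents give no effect size, retention, variance, sample size or sequence ratio, so there is no figure to reproduce. The check is algebra under stated assumptions.

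**Inputs from the protocol:** 6 weeks per period and 8 weeks of wash-out. A period-1 gain is therefore 8 weeks old when period 2 starts and 8 + 6 = 14 weeks old when it ends.

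**Assumptions:** training gain a; added stimulation gain b (the true B − A); gains add; sequences are equal in size; each gain is lost exponentially with half-life h weeks after its arm ends. The retained fractions are r8 = 2^(−8/h) and r14 = 2^(−14/h).

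**Reading 1: change from study baseline**
- Sequence AB: [a + b + r14·a] − a = b + r14·a
- Sequence BA: (a + b) − [a + r14(a + b)] = b − r14(a + b)
- Mean: b(1 − r14/2)

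**Reading 2: change from the end of wash-out in period 2**
- Sequence AB: [a + b − (r8 − r14)a] − a = b − (r8 − r14)a
- Sequence BA: (a + b) − [a − (r8 − r14)(a + b)] = b + (r8 − r14)(a + b)
- Mean: b(1 + (r8 − r14)/2)

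| Half-life (weeks) | r8 | r14 | Reading 1, × b | Reading 2, × b |
|---|---|---|---|---|
| 4 | 0.250 | 0.088 | 0.956 | 1.081 |
| 8 | 0.500 | 0.297 | 0.851 | 1.101 |
| 16 | 0.707 | 0.545 | 0.727 | 1.081 |
| 26 | 0.808 | 0.689 | 0.656 | 1.060 |
| permanent | 1 | 1 | 0.500 | 1.000 |

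The training gain a drops out of both means because the sequences are equal.

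**Period 1 alone:** (a + b) − a = b, whatever the retention.

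**Spread between sequences.** Under reading 1 with permanent retention and a = b, AB gives b + b = 2b and BA gives b − 2b = −b. A paired t-test without a sequence or period term counts this spread as error. For illustration, take n = 10, a = b, and an SD set for 80% power without carryover. Simulated power under reading 1 is 64% at 25% retention, 35% at 50% and 2% at 100%.

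**If order matters.** Let T_AB and T_BA be the total gains by order, with the retained gain stable. Reading 2 gives AB = T_AB − 2a and BA = 2(a + b) − T_BA, with mean b + (T_AB − T_BA)/2. If stimulation makes later training more productive, so that T_BA is the larger, the estimate is biased toward zero by half the difference.

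**Precision of period 1.** With N patients in total, outcome variance σ² and within-person correlation ρ, the variance is 4σ²/N for period 1 and 2σ²(1 − ρ)/N for the crossover. The ratio is 2/(1 − ρ): 4.0 at ρ = 0.5, 6.7 at 0.7 and 10 at 0.8 (ρ assumed).

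**The case against.** A reader might infer that the crossover is valid only if the stimulation effect has vanished by week 8, so that success on objective 3 makes the estimate wrong. The documents do not support that. What must be absent is unequal carryover in the quantity compared. Under reading 2 a fully lasting, stable gain gives exactly b, provided total gain does not depend on order, and the end-of-wash-out measurement needed for it is already scheduled. Objective 3 also sets out to evaluate lasting benefit; it does not assert it.

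Other parts of the opposing case also stand:
- The 6–10% inflation assumes that retained gain keeps fading during six weeks of active therapy. If therapy maintains it, reading 2 has no bias.
- The usual argument that carryover cannot be separated from treatment applies to designs with end-of-period outcomes only. Here the residual before period 2 can be observed by sequence.
- The paired test is not the only between-phase comparison, since the SAP also plans change from the preceding block.
- With equal sequences, b = 0 gives an expected difference of zero under both readings, so this model produces no spurious average benefit.

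These points limit the claim without removing it. The SAP does not adopt the end-of-wash-out reference, and its wording on baseline points more naturally to reading 1. The preceding-block comparison does not say whether its reference is the end of treatment or the end of wash-out. Taken from the end of the preceding treatment, its mean is b(1 + (1 − r14)/2). That is unbiased for a permanent gain but gives 1 + (1 − 0.297)/2 = 1.351 times b at an 8-week half-life. The study design figure was not visible in the text reviewed and may show visit timing.

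**Conclusion.** The concern holds in limited form. The plan looks for lasting benefit, crosses over after a fixed wash-out of unsupported length, and leaves its main contrast without a defined period-2 starting point or any carryover assessment.

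Under the reading closest to the SAP, the expected B − A is attenuated by about 4% to 50% for half-lives from 4 weeks to permanent. Measured from the end of wash-out, it is unbiased for a stable, order-independent gain and inflated by about 6–10% for half-lives of 4 to 26 weeks if fading continues through period 2. Size and direction therefore depend on the reference point and on decay.

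These figures rest on additive gains, equal sequences and exponential loss, none of which the documents state. With unequal sequences the training gain no longer cancels under reading 1. With permanent retention, a = b and one third of patients in AB, the mean is (1/3)(2b) + (2/3)(−b) = 0.

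This should be corrected because it affects the trial's main comparison at little cost. It does not show that the crossover is invalid.

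**What to change.** Add three statements to the SAP:
1. Each period's change is taken from the measurement just before that period: the Phase I baseline for period 1, and the already scheduled end-of-wash-out measurement for period 2.
2. The period-1 comparison (change to the end of the first 6-week arm, B-first versus A-first) is always reported with its confidence interval beside the crossover estimate and its interval. No carryover pre-test chooses between them.
3. The residual above baseline at the end of wash-out is reported by sequence and stated as a limit on the crossover estimate.

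I would not make a superiority conclusion depend on the two estimates having the same sign. Every factor in the table is positive (0.50 to 1.10), so sign agreement cannot reveal carryover of this kind. It also costs power. With no carryover, n = 10, 80% paired power and ρ from 0.5 to 0.8 (all assumed), period 1 has the wrong sign in about 6–16% of simulated trials, and power under such a rule falls to about 69–77%.

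The cost is some extra analysis of data already scheduled, with no change to visits, treatment or wash-out. The downside is that the period-1 contrast is much less precise than the paired one, and the conclusion may have to be more guarded.
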